#### **7.1.9. Visit 3, Online questionnaire**

Each participant will be emailed a link to a questionnaire by the study team. The individualised link for the questionnaire can be copied from The HEART Application, which will be available when the report is available for download. It is essential that the link copied from the correct participant ID is sent to the correct participant.

Responses are anonymous and each questionnaire should take around 20 minutes to complete.

If the questionnaire is not completed within 2 weeks, the participant will be reminded of the questionnaire either by re-sending the link by email or by phone contact from the clinical study team. If the questionnaire is still not completed, a further reminder can be sent. One reminder will be the maximum number of reminders allowed per participant. The questionnaire link will be disabled no earlier than 4 weeks after the link was first sent, therefore, each participant is allowed at least 4 weeks to complete the online questionnaire.

The following information will be collected:

- date questionnaire link sent to the participant
- dates of reminders, if applicable
- date of completion
- anonymised questionnaire responses.

#### **7.1.10. Visit 4, Phone interview**

To participate in an interview, the participant must have signed the relevant focus group consent form at visit 1 and completed the online questionnaire at Visit 3. The participant will be informed that they may not be selected as only a small number of interviewees are required. If they are selected, they will be contacted by the study team conducting the Interview to arrange a suitable time. If they are not selected, there will be no further communication.

If a participant is selected for a phone interview, they will be contacted by the qualitative research team.

Consent procedures will be followed as described in section 7.1.5.

With consent, their details will be passed to the qualitative research team to arrange a convenient time for the interview. A discussion guide will be used for the interview.

The following information will be collected:

- consent date
- interview date
- audio recording, transcribed

If the interviewee does not attend the interview, a single attempt will be made to reschedule. Non-attendees will be replaced as required until approx 20- 30 participants are interviewed

#### **7.1.11. Withdrawal criteria**

Participants may be withdrawn from the study at any time for any reason.

Reasons for withdrawal from the study may include, but are not limited to, the following:

- Participant's withdrawal of consent at any time.
- Investigator or Sponsor determines it is in the best interest of the patient.

Participants who wish to withdraw from the study can inform the investigator or study team at any time during the study. Participants who withdraw and who have had specimen samples taken for genetic analysis will not receive their results but their results will be used in the study analyses. A participant that wishes to withdraw before receiving the CVD IRT score will continue to receive their QRISK®2 score as per standard practice.

Reasonable effort will be made to obtain information about participants who withdraw from the study, and the primary reason for withdrawal/discontinuation documented.

The CRF will collect:

- date of withdrawal
- reason for withdrawal if the participant is willing to share.

As described in section 9.2, if a participant has an ongoing serious adverse device effect (SADE) or unanticipated SADE (USADE) at their final visit, follow-up to resolution should be attempted.

Patients who withdraw from the study will not be replaced.

### **7.2. HCP participation**

#### **7.2.1. Screening**

The Sponsor representative will work with qualitative researchers to identify HCPs that are eligible to complete the questionnaire (see section 6.2.1).

#### **7.2.2. Consent**

The online questionnaire includes a preamble to inform the HCP that by completing the questionnaire they are providing consent for the use of their data and responses.

The focus group will require separate and written consent prior to focus group participation.

#### **7.2.3. Schedule**

There will be two questionnaires for HCPs to complete -

- 1) At Visit 2 - When the CVD IRT report has been received and discussion with the participant has taken place, the HCP will be required to complete a focused questionnaire in the eDC.
- 2) When at least  $\frac{1}{3}$  of the site's participants or at least  $\frac{1}{3}$  of the total study participants (whichever is first for each site) have completed Visit 2, the clinical study team will be provided with a link to an online questionnaire, designed specifically for the physicians and nurses who have participated in the clinical study. The questionnaire will take approximately 20 minutes to complete.

The HCPs will be reminded to complete the questionnaire a maximum of two times.

When no more questionnaire responses are anticipated, focus groups will be arranged selecting HCPs from those that have completed the questionnaire.

The timeline of the focus groups will be towards the end of participant participation at site, and the completion of the HCP questionnaires. It is intended that focus groups may be conducted in parallel with the participant interviews. It is anticipated that the interviews will be conducted as close to or just after all participants have completed Visit 2.

### **7.3. PCC participation**

#### **7.3.1. Screening**

The qualitative researcher will identify approximately five PCCs from the North East England Clinical Commissioning Groups (CCGs).

#### **7.3.2. Consent**

The focus group will require written consent prior to focus group participation.

#### **7.3.3. Schedule**

The PCC focus group will be conducted at any time after the HCP questionnaires have been sent out and maybe conducted in parallel with the participant interviews and HCP focus groups.

### **7.4. End of study**

The end of the study is taken as the date of the last participant, last interview (Visit 4). Focus groups with HCPs and PCCs may take place before or after the end of the study.

The end of the study for an individual participant is defined as the date when the participant has completed the online questionnaire, OR for a participant being interviewed as soon as that interview has taken place, unless they have been withdrawn from the study earlier.

The end of the study for an individual GP practice is defined as the date that the last participant has completed Visit 2, the HCPs have completed the online HCP questionnaire OR for a practice participating in the HCP focus group, as soon as that focus group meeting has taken place.

When recruitment is complete, the function to add new participants will be removed from all sites. The HEART application will be kept live until the final reminder for the questionnaire has been

submitted, to allow access to the questionnaire link. Access will be removed on a site by site basis as each site completed study activities.

The final activity of the study is either the final participant Interview, the final HCP focus group of the PCC focus group, whichever comes last.

### **7.5. Storage, analysis and destruction of clinical samples**

A 'Sample Handling and Shipping Instructions Manual' will be provided for sites to instruct on the samples required and how to package for delivery. No sample processing will take place at site and no blood or saliva samples will be stored at site and all samples will be packaged on the day of collection and sent for analysis within 24 hours. No patient identifiable information will be provided with the samples; only the participant ID and sample number/barcode linked to the samples. Samples will be tracked and monitored through to destruction.

#### **7.5.1. Biosample processing**

Biosample processing and the generation of the genetic data will take place in contracted research laboratories following laboratory standard operating procedures (SOPs) and Sponsor's instructions.

Anonymised samples collected from consenting participants will be transported to separate UK laboratories (one for blood, one for saliva) where DNA will be extracted from the samples. Blood and saliva DNA, only sufficient for analysis and no more, will be transported to a single genotyping laboratory in the US for genetic analysis. The resulting DNA sequences (electronic files) will be returned to Genomics plc in the UK.

Anonymisation of samples will be maintained throughout sample processing.

[figure not shown]
#### **7.5.2. Genetic data analysis**

##### **Blood samples**

On receipt of the individual genetic results, analysis of genetic data will take place at Genomics plc. Individual level CVD IRT reports will be generated for each participant and returned to the GP practice.

##### **Saliva samples**

DNA extracted from the saliva samples will be used for exploratory purposes only to understand whether DNA extracted from saliva can provide comparable results.

**Figure 4: Transport and processing of study samples.**

#### 7.5.3. Sample destruction

The DNA will be extracted from one of the blood samples and the saliva sample at the respective DNA extraction laboratories. The second blood sample will be stored in case of quality failure with the initial blood sample.

The DNA will be stored at the extraction lab, with only sufficient DNA for analysis sent to the Genotyping laboratory in the US. Excess DNA will be stored at the UK DNA extraction laboratories in case replacement samples are required. At the end of the study, any and all unused DNA and remaining blood and saliva samples will be destroyed when genetic analysis for the study is complete, on the sponsor's instructions.

The DNA sequence (now electronic data) will be sent to Genomics plc to calculate the PRS, and to determine the CVD IRT score.

#### 7.5.4. Future research

The anonymised genetic data (electronic only) will be kept for future research, and this will be clearly set out in the participant consent forms. If the participant does not agree to their genetic data being kept for future work, they will not be able to participate in the study.

## 7.6. Qualitative assessments

The study uses questionnaires, interviews and focus groups as qualitative assessments.

### 7.6.1. Questionnaires

Visit 1 (baseline): Participants will be asked to complete a paper questionnaire consisting of four questions. Participants will complete after the study procedures have been completed and just prior to leaving the GP Surgery. The study staff will enter the data into the eCRF and keep the questionnaires filed in the site file as source data.

Visit 2: HCPs will be asked to complete a focused questionnaire via the eDC.

Visit 3: An online questionnaire (using SurveyMonkey) will be sent to study participants and HCPs to complete. The questionnaires, different for participants and HCPs, are mixed qualitative and quantitative questionnaires designed to capture their understanding and perception of the CVD IRT as well as its usefulness and impact.

All participants who completed Visit 2 will be requested to complete an online mixed quantitative and qualitative questionnaire. A link will be emailed by the site staff to the patients' personal email address up to 14 days after the receiving test results, and patients will be reminded once to complete the questionnaire. If there is no response after 4 weeks, the questionnaire will be closed to the participant. The target minimum response rate is 20%.

All HCPs involved in the study will be emailed a link to the HCPs' work email address after at least  $\frac{2}{3}$  of that site's participants or at least  $\frac{2}{3}$  of the total study participants (whichever is first for each site) have completed visit 2. HCPs will be reminded to complete the questionnaire no more than twice. HCPs are expected to respond to the questionnaire within three weeks of issue. The target response rate is 50%.

### 7.6.2. Interviews

From the questionnaire respondents, a sample of participants will be selected by NECS for semi-structured individual telephone interviews (which will be recorded) lasting approximately 30 minutes in length.

The interview process will take place 1-2 months after a participant has completed their survey. Participants who consent to participate in these interviews will be selected to represent a purposive sample from a variety of practices and areas within the study. A total of 20-30 participants will be interviewed (the final number will be dependent upon total interview recruitment figure) via telephone with the aim of undertaking up to 2 months after test results are returned.

Interview topics will be structured around the relevant outcome measurements of the key study objectives. Detailed interview questions will be developed and guided by the data received from online questionnaires and agreed with the Sponsor before the interviews take place.

For example, patients may be asked about:

- Study process - Level of satisfaction in experience
- Study report results - Level of satisfaction in outcome

- Communication – Before and during the testing and results process

The interviews will be recorded. The content will be analysed using thematic analysis. These findings will present anonymised patients' perspectives and experiences and will be triangulated with the online questionnaire and quantitative data collection.

NECS will provide anonymised typed transcripts from the recordings of the interviews and thematic analysis will be provided to Genomics plc. Audio recordings will be destroyed once transcriptions have been analysed.

### **7.6.3. Focus Groups**

#### **7.6.3.1. HCP**

The HCP focus groups will follow the completion by HCPs of the online questionnaire. HCPs will be asked to provide and sign consent for the release of typed anonymised transcripts from the recordings of the focus groups to NECS and thematic analysis provided to Genomics plc.

NECS will run an online focus group(s) of around 15 HCPs from a number of practices. The number is dependent upon the total recruitment figure and will be run until saturation is reached). The focus groups will last 45 - 60 minutes in length and be held online (e.g. Zoom/Teams) after the majority or all of the HCP questionnaires have been returned. There may be an option to incorporate this into a weekly practice meeting for HCP convenience. Dependent on recruitment, and subject to responses, a separate focus group(s) may be organised for nurses involved in the study.

Interview topics will be structured around the relevant outcome measurements of the key study objectives. Detailed interview questions will be developed and guided by the data received from online questionnaires and patient interviews, and agreed with the Sponsor before the interviews take place.

For example, HCPs may be asked about:

- Set-up - Incorporating the test into practice systems and initial approach to patients
- Communication – Exchanges with patients and Genomics plc
- Results - Level of satisfaction and perception of the process of obtaining and communicating results to patients
- Implementation - Consideration of genetics as a risk factor in primary care
- Usefulness - Value of genetics as a risk factor for cardiovascular disease

The focus groups will be recorded. The content will be analysed using thematic analysis. These findings will present HCPs anonymised perspectives and experiences and will be triangulated with the online questionnaire and quantitative data collection.

#### **7.6.3.2. PCCs**

Primary Care Commissioners (PCCs) (<5) will be recruited from Northeast England Clinical Commissioning Groups (CCGs) to understand their views on potential implementation. They will be invited to a separate focus group 45-60 minutes in length. The session will take place in parallel with the HCP focus groups.

Attending PCCs will be asked to provide and sign consent for the release of typed anonymised transcripts from the recordings of the focus groups.

Interview topics will be structured around the relevant outcome measurements of the key study objectives. Detailed interview questions will be developed and guided by the data received from online questionnaires, patient interviews and HCP focus groups, and agreed with the Sponsor before the interviews take place.

For example, Primary Care Commissioners may be asked about:

- Acceptability of the test in the current primary care setting
- Implementation of genetics as a risk factor in primary care
- Usefulness of genetics as a risk factor.

Audio recordings will be analysed using thematic analysis. These findings will present PCCs' anonymised perspectives and experiences.

## 8. CONCOMITANT MEDICATIONS

No data on participant concomitant medications will be collected for this study.

Participants who are required to start statin treatment based on the CVD risk assessment score provided at visit 2 will be able to do so.

## 9. SAFETY MONITORING

### 9.1. Definitions

#### 9.1.1. Adverse Events and Device Deficiency

The adverse event and device deficiency definitions are aligned to those in the international standard ISO 20916: 2019 for in vitro diagnostic medical devices, allowing for CVD IRT being a risk assessment tool rather than a diagnostic tool.

Term	Definition
Adverse Event (AE)	Any untoward medical occurrence, inappropriate patient management decision, unintended disease or injury, or untoward clinical signs, whether or not related to the IVD or study procedures.
Serious Adverse Event (SAE)	AE that led to any of the following 
 
a) death
 
b) serious deterioration in the health of the participant as defined by one or more of the following               
 
i) a life-threatening illness or injury, or
 
ii) a permanent impairment of a body structure or a body function including chronic diseases, or
 
iii) in-patient of prolonged hospitalisation, or
 
iv) medical or surgical intervention to prevent life-threatening
 
 
 

	illness or injury or permanent impairment to a body structure or a body function c) foetal distress, foetal death or a congenital abnormality or birth defect including physical or mental impairment
Adverse Device Effect (ADE)	AE related to the use of an IVD.
Serious Adverse Device Effect (SADE)	ADE that has resulted in any of the consequences characteristic of a SAE
Unanticipated Serious Adverse Device Effect (USADE)	SADE which by its nature, incidence, severity or outcome has not been identified in this protocol.
Device deficiency	A device deficiency is an inadequacy of a medical device related to its identity, quality, durability, reliability, usability, safety, or performance, such as malfunction, misuse or use error or inaccurate results and inadequate labelling.

**Table 4: Definitions of AEs and device deficiency.**

The following should not be considered an AE: a condition requiring a pre-planned procedure unless the condition worsened since screening or a pre-existing condition found as a result of screening, unless the condition has worsened since enrolment.

#### **9.1.2. Adverse Event Severity Classification**

An AE can be classified as severe and not deemed a SAE. Similarly, a SAE is not automatically severe in nature.

Severity will be defined according to the following criteria:

Mild	Discomfort noticed, but no disruption of normal daily activity
Moderate	Discomfort sufficient to reduce or affect normal daily activity
Severe	Incapacitating with inability to work or perform normal daily activity

**Table 5:Severity Classification**

#### **9.1.3. Adverse Event Relationship Classification**

Each Adverse Event will be assigned a relationship to the study tool or study procedures. Relationships will be assessed as follows:

Not related	Relationship to the device or procedures can be excluded when there is no temporal relationship, the event is not known for the type of device or procedure, is implausible and other more reasonable explanations are available.
Unlikely	The relationship with the use of the device or procedures seems not relevant and/or the event can be reasonably caused by another cause.
Possible	The relationship with the use of the device or procedures is weak but cannot be ruled out.
Probable	The relationship with the use of the device or procedures cannot be reasonably explained by another cause.
Causal relationship	The event is associated with the device or procedures when there is a temporal relationship, the event is known for the type of device or procedure, and no other reasonable explanation is available.

**Table 6: Definitions of relationship to device or procedure**

#### **9.1.4. Adverse Event Outcome Classification**

Outcome of the event will be defined according to the following:

Resolved:	The event was fully resolved at the end of the study.
Resolved with sequelae:	The event has resolved, but retained pathological conditions resulting from the results and presentation.
Continuing:	The event is ongoing at the end of the study.

Death:	This event is determined to be the cause of death.
---------------	--

**Table 7: Event outcomes.**

## 9.2. Adverse Event Recording

Adverse event monitoring outlined in this protocol is reflective of the risk/benefit ratio of participating in the study to the patient. Intervention is minimal; an additional blood sample and saliva sample for a subgroup, the participant will receive a second CVD risk score in addition to the standard CVD QRISK®2 score, followed by an online questionnaire (and possible interview). All these activities are considered low risk.

To this end, the study will only collect adverse events considered related to study procedures or the risk assessment tool (CVD IRT). In addition, since all participants will provide a blood sample as part of standard practice (for QRISK®2), the study is requesting that study blood samples be collected using the same venepuncture. Therefore, mild events such as the following which are common when giving blood samples will not be collected for the study safety database:

- Pain
- Feeling faint
- Bruising
- Minor bleeding
- Haematoma
- Site infection

However, adverse events due to the process of blood sampling that are not common or are severe in nature will be collected. The WHO Best Practices for Injections and Related Procedures Toolkit can be referred to minimise adverse events.

From point of consent to collection of results at visit 2, all AEs considered related to the risk assessment tool or study procedures will be collected during visit 2 by the clinical team. At visit 3, the online questionnaire will be reviewed by the qualitative research team to identify related AEs and reported to the clinical team for documentation.

Similarly, during interviews, the qualitative research team (interviewer) will again identify related adverse events, but in this instance only those meeting the criteria of 'serious' will be collected. All SAEs will be forwarded to the clinical team for documentation.

Throughout the study, the participant will be invited to contact the study team at any time to discuss any concerns and issues raised by the study, and any related AEs identified will be collected as described above. Up to the point of online questionnaires, self-reported related adverse events will be collected and after the online questionnaires, self-reported related adverse events meeting the criteria of 'serious' will be collected until study end. Related SAEs should be followed to resolution if possible.

All adverse events must be recorded in the eCRF as soon as possible.

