### **9.4. Recording and Reporting Responsibilities**

#### **9.4.1. Investigator Responsibilities**

The investigator and study team are responsible for collecting AEs as described in section 9.2 using the eCRFs (AE log and SAE page ) within 24 hours of learning of the event. The investigator is responsible for reviewing all AEs and SAEs.

AEs will also be recorded in the participant medical notes.

The investigator is responsible for assigning seriousness and relationship to the risk assessment tool or study procedures and document this in the eCRF. If this is not available immediately, the initial report using the paper backup should be submitted to [REDACTED] and follow-up information reported as soon as possible, in a timely manner.

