#### **9.4.2. Qualitative Researcher Responsibilities**

ADEs and SADEs identified by the qualitative research team will be collected and shared with the clinical study team at site immediately upon identification to then be entered into the eCRF. The qualitative research team will review questionnaires on a regular basis to ensure appropriate and timely reporting.

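### The qualitative team screens post-score adverse events for relatedness and seriousness, judgements the protocol gives to the investigator, and no clinical review of unforwarded events is planned

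*Protocol*

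**What the plan says.** Protocol 9.2 limits collection to events considered related to the tool or the study procedures. Up to Visit 2 the clinical team collects them. After that the work passes to the qualitative research team:

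- **Visit 3 questionnaire (9.2):** "At visit 3, the online questionnaire will be reviewed by the qualitative research team to identify related AEs and reported to the clinical team".
- **Visit 4 interview (9.2):** the interviewer "will again identify related adverse events, but in this instance only those meeting the criteria of 'serious' will be collected". The next sentence adds: "All SAEs will be forwarded to the clinical team for documentation".
- **Handover (9.4.2):** "ADEs and SADEs identified by the qualitative research team will be collected and shared with the clinical study team at site immediately upon identification", for entry into the eCRF.

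Protocol 9.4.1 places the judgement elsewhere: "The investigator is responsible for assigning seriousness and relationship to the risk assessment tool or study procedures". It also makes the investigator responsible for reviewing all AEs and SAEs.

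On the questionnaire itself, Protocol 7.1.9 states: "Responses are anonymous and each questionnaire should take around 20 minutes to complete". The same section describes an individualised link taken from the participant's own ID. SAP 4.1 refers back to Protocol 9.2 for collection and lists events as reported.

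**The concern.** Two sets of people appear to hold the same judgement. If the qualitative team decides what is related (and at interview what is serious) before anything is sent to the site, the investigator's responsibility under 9.4.1 covers only what has passed that first filter.

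The timing makes this matter. Protocol 9.2.1 anticipates anxiety and distress, including after the score is received. Those reactions would surface after Visit 2, when the scheduled contacts are the ones the qualitative team reads. Secondary objective 9 is measured by the number and nature of adverse events recorded, so events stopped at the filter are missing from the outcome.

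**Working it through.** The documents state no figure on this point, so the check is a comparison of sections.

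1. **What the label carries.** Protocol 9.1.1 defines an ADE as an AE related to use of the IVD, and a SADE as an ADE with serious consequences. A team that passes on ADEs and SADEs (9.4.2) has already taken a view on relationship, and for SADEs on seriousness.

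2. **What threshold applies.** Protocol 9.1.3 gives five levels of relationship, from not related to causal. Neither document says which level counts as related for the qualitative team's screening, and no low referral threshold is set.

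3. **Who decides.**

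| Contact | Reads first | Criterion before the site sees it | Formal responsibility (9.4.1) |
|---|---|---|---|
| Up to Visit 2 | Clinical team | Related | Investigator |
| Visit 3 questionnaire | Qualitative team | Related | Investigator |
| Visit 4 interview | Qualitative team | Related and serious (or serious only, see step 4) | Investigator |

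The last two rows do not agree with themselves.

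4. **The interview wording has two readings.** The first sentence and 9.4.2 point to events that are both related and serious. The following sentence speaks of all SAEs, and 9.1.1 defines an SAE through the AE, which need not be related. Taken literally, every serious event is forwarded. On either reading the interviewer judges seriousness.

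5. **Direction of error.** An event forwarded in error can be reclassified by the investigator. An event wrongly held back is not presented for classification. Errors at the screening step therefore lower the count and do not raise it.

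6. **Other routes to the site.** Protocol 9.2 invites participants to contact the study team at any time; after the questionnaire only serious related self-reports are collected. Protocol 11.4 keeps questionnaire responses and transcripts for at least 10 years. Neither Protocol 9 nor SAP 4.1 or 7.7 plans a clinical re-read of that text.

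7. **What can be counted.** The undercount would be

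   texts screened × share mentioning an untoward event × share of those wrongly held back.

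   Only the first factor can be approached. Protocol 7.6.1 sets a target minimum response of 20% among participants who completed Visit 2. If all 1000 did so, 1000 × 0.20 = 200 questionnaires. Attrition lowers this number and a better response raises it. Between 20 and 30 of the respondents are also interviewed. The other two factors are not in the documents, so the product cannot be computed.

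**The case against.** The strongest reply is that 9.4.1 has the investigator collect events in the manner of 9.2 and then classify them, so the plan can be read as two steps: the qualitative team flags and the investigator decides. No section asks the team to use the five-level scale or to record causality. Collecting only related events is also a deliberate and reasonable choice in a low-risk study. Both points stand. But the two-step reading works only for events that are forwarded, and the stated criterion for forwarding is relatedness. The collection rule can be kept while changing who applies it.

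A reader might infer more than the documents support:

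- **That screened-out events cannot reach the investigator or be audited.** Participants can contact the study team directly, the text is retained and may be destroyed only with the sponsor's agreement, and Protocol 12 requires a monitoring plan covering source data and safety reporting, whose content is not shown. What can be said is that no clinical review is planned in the documents at hand.
- **That the readers are clinically unqualified.** Their qualifications and safety training are not stated. It is a fair inference that they work without the medical notes, since Protocol 7.1.7.1 collects no medical history details and 11.2 keeps personal details with practice staff and, on request, sponsor monitors.
- **That a number of missed events can be given.** Assuming that 5% to 10% of 200 questionnaires mention an event gives 10 to 20 mentions. That rate is not in the documents, and it counts mentions, not events wrongly held back.

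**Conclusion.** The inconsistency is real and the concern holds in a limited form. Sections 9.2 and 9.4.2 put a relatedness screen, and at interview a seriousness screen, ahead of the investigator to whom 9.4.1 assigns both judgements. Nothing planned picks up what the screen holds back. The adverse event count for secondary objective 9 may therefore be too low for the period after the score is given. Collection up to Visit 2 is not affected.

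The size of the undercount is unknown and could be small. The conclusion does not depend on the number of questionnaires, on a mention rate or on the team's qualifications. It rests on the wording of the three sections and on no clinical check appearing in either document; a monitoring plan or working instruction that is not shown could supply one.

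**What to change.** Reconcile Protocol 9.2, 9.4.1 and 9.4.2:

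- The qualitative team forwards every possible untoward event found in a questionnaire or interview to the site, with the participant ID, without judging relatedness or seriousness.
- The investigator assigns both under 9.4.1 and then applies the existing collection rules unchanged: related events up to the questionnaire, related and serious ones after it.
- In 7.1.9, describe the Visit 3 responses as pseudonymised by participant ID. The individualised link already ties them to that ID, and an event cannot be routed to the right site without it. Section 11.1, which calls the same survey data anonymised, should be aligned.

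The cost is a small number of extra reports for sites to review, most of them probably unrelated, and a protocol amendment, which goes to the REC and HRA if substantial (Protocol 16). If participants have been told that their answers are anonymous, the participant materials may need matching changes; those materials are not among the documents available.
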